STATISTICAL ANALYSIS PLAN

Official title: iSTAND: IVIG (Gamunex-C) Study of Treatment for Autoimmune Neuropathic Dysautonomia/Postural Tachycardia (POTS)

NCT number: NCT03919773

Document date: October 26, 2023

STATISTICAL ANALYSIS PLAN

This study was powered to determine a difference between treatment groups for the COMPASS-31 change from baseline assuming the IVIG group would have a 15-point decrease and the Albumin group would have a 4-point decrease with a pooled standard deviation of 10.0. These estimates were based on reported changes in POTS patients treated with IVIG and accounted for an estimated 7% dropout rate. Based on these, sample sizes of 14 per group achieved 80% power to detect this difference (effect size of 1.1) using a two-sided two-sample t-test and assuming a significance level of 0.05.

After a six-week washout, subjects who completed the protocol were allowed to continue into a second treatment phase to receive the other treatment using an identical infusion schedule, with both participants and investigators remaining blinded to treatment assignment. This second phase treatment option was included in the protocol to improve recruitment but was not part of the primary study outcome. Data for phase 2 (which included 23 of 30 participants) was analyzed separately.

Data from all participants who began treatment were analyzed in an intention-to-treat analysis using Kruskal-Wallis test for COMPASS-31 score change (primary) and other non-parametric ordinal variables. Fisher exact tests were used for dichotomous variables such as symptomatic outcome (COMPASS-31 score improved/worsened by 20%). Summary statistics for continuous variables were reported with means and standard deviations if normally distributed, medians and interquartile range if non-normally distributed. Summary statistics for categorical variables were reported as counts and column percentages. Outcomes were evaluated both as "intention-to-treat" (ITT, including 28 evaluable participants) and "per-protocol" (including only the 27 who completed > 85% of study treatments per protocol).

Document Date: October 26, 2023

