Gammunex-C, a form of intravenous immunoglobulin (IVIG), is approved for the treatment of chronic inflammatory demyelinating neuropathy (CIDP) or idiopathic thrombocytopenic purpura (ITP) (see attached package insert). IVIG has been in use for many decades in the treatment of these disorders and many other inflammatory/autoimmune diseases. It is generally very safe and well tolerated. More recently, IVIG has been proposed as an effective treatment for presumed inflammatory neurological disorders which do not meet the criteria for CIDP. Specifically, case reports and cases series have indicated therapeutic responses to IVIG in autonomic neuropathies. (See Goodman, B. P. (2017). "Immunoresponsive Autonomic Neuropathy in Sjogren Syndrome-Case Series and Literature Review." Am J Ther doi: 10.1097/MJT.00000000000583. and Oaklander, A. L. (2016). "Immunotherapy Prospects for Painful Small-fiber Sensory Neuropathies and Ganglionopathies." Neurotherapeutics 13(1): 108-117).

Intravenous Albumin is approved for the treatment of hypovolemia (see attached package insert). The use of albumin to increase plasma volume in patients with POTS has been suggested. In this study, albumin will be used as an active control treatment to provide the same volume and protein load as IVIG but without the immunomodulatory effects.

Significance: There have been few well designed clinical therapy trials aimed at POTS patients and even fewer that are aimed at a particular pathophysiological subtype of POTS. Evidence suggests that POTS is a heterogeneous disorder with differing underlying mechanisms. Several uncontrolled case series have suggested a benefit of IVIG for POTS, but the volume expansion associated with infusion of IVIG make it difficult to assess the immunomodulatory effects of this treatment. We propose to evaluate the efficacy of IVIG using a double-blind randomized cross over design that will determine efficacy while reducing effects of inter-subject variability and placebo effect which are common problems in POTS therapy research. Even with the statistical advantages of a crossover design, the treatment cohort will be small, and this study is designed to be a pilot (phase II) study to evaluate the feasibility, tolerability and potential benefits of treatment. The results of this pilot study will provide the impetus and rationale for a larger multicenter clinical trial to definitively evaluate immunomodulatory treatment in POTS.

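### The 80% power is right for the t-test it names, but the primary test is Kruskal-Wallis, which has about 78% at the same inputs if changes are normally distributed

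*SAP*

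**What the plan says.** The first paragraph of the SAP sizes the trial on change from baseline in COMPASS-31, "assuming the IVIG group would have a 15-point decrease" and "the Albumin group would have a 4-point decrease with a pooled standard deviation of 10.0". It concludes that "sample sizes of 14 per group achieved 80% power to detect this difference (effect size of 1.1) using a two-sided two-sample t-test", at a significance level of 0.05. It adds that the estimates "accounted for an estimated 7% dropout rate", without saying whether 14 per group is counted before or after dropout.

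The third paragraph of the SAP names a different test for the primary outcome, "using Kruskal-Wallis test for COMPASS-31 score change (primary) and other non-parametric ordinal variables". No power is given for that test. The SAP also reports 30 participants in total and 28 evaluable in the intention-to-treat analysis.

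**The concern.** A power figure belongs to a particular test. With two groups, Kruskal-Wallis is the Wilcoxon-Mann-Whitney rank-sum test, and for normal data it is somewhat less efficient than the t-test. The t-test calculation has no margin: 14 per group gives 80% almost exactly. Any loss of efficiency therefore takes the planned analysis below the stated figure under the model used for sizing.

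What is at stake is how a non-significant primary result would be read. A reader would take 80% as the power of the analysis that was run, when it was calculated for another one.

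**Working it through.** **Inputs, all from the SAP.** Mean falls of 15 (IVIG) and 4 (albumin) points, "pooled standard deviation of 10.0", 14 per group, two-sided alpha 0.05, 7% dropout, 30 participants, 28 evaluable.

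**Step 1: reproduce the stated figure.**
- Standardised difference: d = (15 − 4)/10 = 1.1, matching the SAP's "effect size of 1.1".
- Degrees of freedom: 14 + 14 − 2 = 26, so the critical t is 2.056.
- Noncentrality: d × √(n/2) = 1.1 × √7 = 2.910.
- Power from the noncentral t distribution: 79.99%. The stated 80% is correct for the t-test.

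**Step 2: power of the primary test, normal data.** Kruskal-Wallis was simulated with 400,000 trials per setting, a pure shift of 1.1 SD and the chi-square p-value on 1 df.
- 14 v 14: 77.7% to 77.8%. The rejection rate under no difference is 4.97%, so the test holds its size.
- Analytic cross-check: the asymptotic relative efficiency of the rank-sum test for normal data is 3/π, so 14 per group acts like 14 × 3/π = 13.37 per group for a t-test. The noncentral t formula then gives 78.0%.
- Difference needed for 80%: power is 79.9% at 11.3 points and 80.7% at 11.4. To one decimal, 11.4 is the first value above 80%.

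**Step 3: the same test with other shapes.** SD, shift and 14 per group are held fixed. These shapes are assumptions, as the documents do not give the distribution of changes.

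| Distribution of changes | t-test | Kruskal-Wallis |
|---|---|---|
| Normal | 80.0% | 77.7% |
| Logistic | 80.1% | 81.6% |
| t with 5 df | 80.9% | 85.1% |

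The rank test loses about 2 points for normal data and gains for the heavier-tailed shapes.

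**Step 4: what 14 per group means.**
- If 14 is the evaluable number, enrolment is 28/0.93 = 30.1. In the other direction, 30 × 0.93 = 27.9. Both match the SAP's 30 participants and 28 evaluable.
- If 14 is the enrolled number, 14 × 0.93 = 13.02 per group remain. Power at 13 per group with normal data is 76.8% for the t-test and about 74.5% for Kruskal-Wallis.
- The second reading cannot be excluded from the wording. The normal approximation gives 13 per group, and 13/0.93 = 13.98 rounds up to 14. The reported counts still favour the first reading. The 28 is given only as a total, so an even split of 14 and 14 is assumed.

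**Step 5: optional sensitivity figures.** With normal data, 14 per group and SD 10, Kruskal-Wallis power is about 61% for a 9-point difference and about 41% for a 7-point difference. These would correspond to albumin falls of 6 or 8 points with IVIG fixed at 15 (15 − 6 = 9; 15 − 8 = 7). Both falls are assumptions.

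**The case against.** The strongest reply is that nothing is miscalculated. The SAP names the test to which its 80% belongs, and for that test it is right. Sizing on a t-test and analysing by ranks is common, the loss under normality is about 2 points, and that is small beside the uncertainty in the assumed effect and SD. A rank test is usually chosen because normality is doubtful, and there it can have more power than the t-test. All of this stands. It limits the point to a missing statement and leaves no error in the sample size.

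Three stronger readings are tempting, and the documents do not support them.

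- **That the trial had less power than it claimed.** This follows only for normal data. The SAP itself provides for non-normal variables in its summary statistics, and for the heavier-tailed shapes in the table Kruskal-Wallis exceeds 80%.
- **That the real power was about 74%.** This requires 14 to be the number before dropout, which the SAP's own counts disfavour. Most of that fall would also come from the lost patients and not from the choice of test: the t-test alone drops from 80.0% to 76.8% at 13 per group.
- **That the albumin assumption is wrong.** The SAP attributes its estimates to reports in IVIG-treated patients and names no separate source for the 4-point albumin fall. The Protocol's Background section says of uncontrolled series that "the volume expansion associated with infusion of IVIG make it difficult to assess the immunomodulatory effects of this treatment", and section 4.a expects the orthostatic intolerance subscore to improve in both arms. That is a reason for interest in smaller differences. It does not show that 4 points is wrong: the source reports cannot be seen here, the albumin control is the design's answer to the volume problem, and section 4.a also plans an analysis without that subscore.

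**Conclusion.** The point holds as a small mismatch between the stated power and the primary test. At the SAP's own inputs, 14 evaluable patients per group give about 78% power for Kruskal-Wallis against the 80% quoted for the t-test, a gap of about 2 points (or 11.4 against 11 points detectable at 80%). This rests on normally distributed changes, a pure shift between groups and an even 14/14 split. With heavier tails at the same SD, power would be about 82% to 85%, so the sign of the discrepancy is not fixed. The finding does not call for more patients.

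**What to change.** Keep the t-test sentence unchanged, since it records how the trial was sized. After the sponsor confirms that 14 is the evaluable number, add after it:

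*For the primary Kruskal-Wallis test, 14 evaluable patients per group give about 78% power for an 11-point difference (SD 10) if changes are normally distributed; about 30 were enrolled to allow for 7% dropout.*

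Power at smaller differences (about 61% at 9 points and 41% at 7 points) may be added, labelled as a sensitivity assumption.

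Do not bring the two into line by making a comparison of means the primary analysis. The SAP describes its analyses in the past tense and reports evaluable and per-protocol counts, so that would change the primary test after the data had been analysed.

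The cost is one sentence in the SAP and a stated power that is slightly less favourable. No patients, data or analyses are added.
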